Plasma MK-1454 PK	X			X				X^{b}	Collect predose samples 1-8 h before MK-1454 administration on C1D1 and C2D1. Collect postdose samples on C1D1 and C2D1 at the following time points: end of IT injection (up to +15 min), 0.5 h (±15 min), 1.0 h (±15 min), 1.5 h (±15 min), 4 h (±15 min), and 6 h (±15 min). Additional postdose samples will be collected at 12 h (±4 h) and 24 h (±4 h) following MK-1454 IT administration on C1D1 only. Collect samples at the same time as for cytokines and CRP, and for pembrolizumab PK, when feasible.
Serum for Pembrolizumab PK	X			X				X	Collect samples predose 0 to 4 h before pembrolizumab IV infusion
Serum for ADA	X			X				X	on C1D1, C2D1, C4D1, and on Day 1 of every 4 cycles thereafter (ie, C8, C12, etc.). Collect with plasma samples for MK-1454 PK when feasible.
Blood for Plasma Biomarker Analysis				X				X	Collect prior to MK-1454 administration (Arm 1) and prior to pembrolizumab administration (Arm 2 and Arm 3) on C2D1 and
Blood for Serum Biomarker Analysis				X				X	C5D1.

087V73

Protocol/Amendment No.: 001-08

Trial Period	Treatment Phase MK-1454 Monotherapy Cycle = Classical then Q3W MK-1454 and Pembrolizumab Combination Therapy Cycle = 21 Days								
Cycle	Cycle 1		Cycle 2			Cycle 3	Cycle 4 and Beyond	Notes	
Scheduling Day	1	8	15	1	8	15	1	1	
Scheduled Window	±3	±3	±3	±3	±3	±3	±3	±3	
Blood for RNA Analysis	X								Collect predose 0-4 h before MK-1454 administration on C1D1 Collect postdose 6 h (±15 min) after MK-1454 administration on C1D1.
Blood for Genetic Analysis ^c	X								Collect prior to treatment.
Tumor Tissue Biopsy ^d							X	X	For the tumor lesion that is treated with IT administration of MK-1454, collect predose tumor biopsy on the same day as treatment prior to IT administration of MK-1454 on C3D1, or up to 3 days prior to treatment on C3D1, and optionally on C6D1 prior to IT administration of MK-1454, or up to 3 days prior to treatment on C6D1. If available, biopsy of a distant, discrete, noninjected site is preferred on the same day as the IT administration of MK-1454 but may be performed up to 3 days after treatment of the injected lesion. The C6D1 biopsy time point is encouraged, but optional.

ADA = antidrug antibodies; AE = adverse event; aPTT = activated partial thromboplastin time; CBC = complete blood count; CRP = C-reactive protein; CT = computed tomography; CTCL = cutaneous T-cell lymphoma; DNA = deoxyribonucleic acid; ECG = electrocardiogram; ECOG = Eastern Cooperative Oncology Group; FBR = future biomedical research; GGT = gamma glutamyl transferase; hCG = human chorionic gonadotropin; HIV = human immunodeficiency virus; HNSCC = Head and Neck Squamous Cell Carcinoma; HPV = human papillomavirus; IEC = Institutional Ethics Committee; INR = international normalized ratio; IRB = Institutional Review Board; irRECIST = immune-related RECIST; ISCL = International Society for Cutaneous Lymphomas; IT = intratumoral; LDH = lactate dehydrogenase; MRI = magnetic resonance imaging; PET = positron emission tomography; PT = prothrombin time; PTT = partial thromboplastin time; RECIST v1.1 = Response Evaluation Criteria In Solid Tumors, version 1.1; RNA = ribonucleic acid; (F)T3 = (free) triiodothyronine; (F)T4 = (free) thyroxine; TSH = thyroid-stimulating hormone; WOCBP = women of childbearing potential.

- a) The inpatient observation period may be extended up to 48 hours at the discretion of the investigator, per local IRB/IEC, and/or Health Authority mandate.
- b) Up to 2 additional serum samples may be collected if deemed medically necessary (eg, in the setting of an AE).
- This sample will be drawn for genetic variations in ADME and planned analysis of the association between genetic variants in DNA and drug response. If the IRB/IEC does not approve of the planned analysis of the association between DNA variation and drug response, or if there is a local law or regulation prohibiting the same, data analysis will be limited to investigate ADME genetic variations. If the sample is collected, leftover extracted DNA will be stored for FBR if the participant (or their legally acceptable representative) provides documented informed consent for FBR. If the planned genetic analysis is not approved, but FBR is approved and consent is given, this sample will be collected for the purpose of FBR.
- All subjects will be required to provide a sample biopsy of the tumor to be injected with MK-1454 and a sample biopsy from a distant, discrete noninjected site (at least 2 biopsies at each site), unless deemed medically unsafe by the investigator. The sample will be obtained by ultrasound guidance or cross-sectional imaging (CT/MRI) guidance. Method of biopsy will be per guidance of the investigator as well as discussion with the Sponsor. Instructions for tissue collection, processing, and shipment are provided in the Procedures Manual. Leftover main study tissue will be stored for FBR if the subject consents to FBR. Instructions for tissue collection, processing, and shipment are provided in the Procedures Manual.

Protocol/Amendment No.: 001-08

6.1.4 Discontinuation / End of Treatment and Posttreatment Follow-up for Arms 1 to 3

		Posttreatm 30-Day Safety	ent Period Survival	
Trial Period	EOT/ Discontinuation	Follow-up Visit	Follow-up	Notes
Scheduling Day		30 days post last dose	Q12W	
Scheduled Window	±7	+7	±14	
Administrative Procedures				
Prior Medication and Concomitant Medication Review	X	X		
Efficacy Procedures				
Tumor Imaging, RECIST, irRECIST, and/or itRECIST Response Assessment	X			
Medical Photography (Cutaneous Lesions)	X			
IWG Revised Response Criteria for Lymphoma (excluding CTCL)	X			
CTCL Response Criteria	X			
Survival Status Monitoring	\	Updated survival status may be requested by the Sponsor at any time during the course of the study. Upon Sponsor notification, all subjects who do not/will not have a scheduled study visit or study contact during the Sponsor defined time period will be contacted for their survival status (excluding subjects that have a death event previously recorded).		
Safety Assessments and Procedures	See Procedures Manual for collection and management of samples.			
AEs Monitoring	X	X		
Full Physical Examination	X	X		
Weight	X	X		
12-lead ECG		X		T 1
Vital Signs	X	X		Temperature, pulse, respiratory rate, blood pressure, and O ₂ saturation
ECOG Performance Status	X	X		
CBC with Differential	X	X		
Chemistry Panel	X	X		
Lipase and Amylase	X	X		

MK-1454-001-08 Final Protocol
087V73
Confidential

Protocol/Amendment No.: 001-08

		Posttreatm	ent Period	
Trial Period	EOT/ Discontinuation	30-Day Safety Follow-up Visit	Survival Follow-up	Notes
Scheduling Day	EO 17 Discontinuation	30 days post last dose	Q12W	Hotes
Scheduled Window	±7	+7	±14	
Pregnancy Test for WOCBP – Urine or Serum hCG		X		For WOCBP, perform as required locally. If a urine pregnancy test cannot be confirmed as negative, a serum pregnancy test is required.
Thyroid Function (TSH, T3, FT3, T4, FT4)		X		
PK/Pharmacodynamics/ Future Biomedical Research	n/Biomarkers			See Procedures Manual for collection and management of samples.
Serum for Pembrolizumab PK	X			Only for pembrolizumab-treated
Serum for ADA	X			subjects.
Blood for Plasma Biomarker Analysis	X			
Blood for Serum Biomarker Analysis	X			

ADA = antidrug antibodies; AE = adverse event; CBC = complete blood count; CTCL = cutaneous T-cell lymphoma; DNA = deoxyribonucleic acid; ECG = electrocardiogram; ECOG = Eastern Cooperative Oncology Group; EOT = end of treatment; (F)T3 = (free) triiodothyronine; (F)T4 = (free) thyroxine; hCG = human chorionic gonadotropin; irRECIST = immune-related RECIST; PK = pharmacokinetic; RECIST = Response Evaluation Criteria In Solid Tumors; RNA = ribonucleic acid; TSH = thyroid-stimulating hormone; WOCBP = women of childbearing potential.

087V73

Protocol/Amendment No.: 001-08

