4.2.3.4 Pharmacodynamic Endpoints

As a required first step in pharmacologic activity, receptor engagement is fundamental to dosing strategies. To evaluate target engagement, a systemic cytokine/chemokine activation assay that compares a panel of cytokine/chemokine activation pre- and post-administration

27-Jul-2021 Confidential

087V73

Protocol/Amendment No.: 001-08

of study drug at both mRNA and protein level has been developed. Additional exploratory analyses will be performed to assess the effect of study drug on immune cells in tumor tissues and in the circulation.

The immediate mediators of CDN STING agonist activity are type I IFNs, proinflammatory cytokines, and chemotactic factors. Thus, systemic cytokines will be monitored to provide information to assist in the evaluation of target engagement and potential safety events associated with immune stimulation and cytokine release. The cytokines that will be assessed include but are not be limited to TNF- α , IFN β , IL-6, MIP-1 α , MCP-2, IP-10, and CXCL11.

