Scheduling Day	1	8	15	1	8	15	1	8	15	1	
Scheduled Window	±3	±3	±3	±3	±3	±3	±3	±3	±3	±3	
CBC with Differential	X	X	X	X	X	X	X	X	X	X	
PT/INR and PTT or aPTT	X			X			X			X	Required within 72 h of C1D1. Does not need to be
Chemistry Panel	X	X	X	X	X	X	X	X	X	X	repeated if screening labs were done within 72 hours of
LDH, GGT	X			X			X			X	C1D1. May be performed up to 72 h prior to dosing for
Urinalysis	X			X			X			X	subsequent cycles when scheduled.
Lipase and Amylase	X			X			X			X	
Pregnancy Test for WOCBP – Urine or Serum hCG	X										Required within 24 h prior to first dose of study medication. Does not need to be repeated if screening test was done within 24 hours of C1D1. If a urine pregnancy test cannot be confirmed as negative, a serum pregnancy test is required. Pregnancy testing must be done as required by local regulation. Where local regulations require monthly pregnancy testing per CTFG guidelines, see Appendix 12.5.
Thyroid Function (TSH, T3, FT3, T4, FT4)	X						X			X	Required within 72 hours prior to Day 1 of C1, C3, C5, C7, C9, C11, and at every other subsequent treatment cycle. Does not need to be repeated if screening labs were done within 72 hours of C1D1.
Pharmacokinetics (PK)/ Pharm	acodyn	amics/	Future	Biome	dical R	esearch	n/Biomai	rkers			See Procedures Manual for Collection and Management of Samples.
Serum for Cytokine Panel and CRP for MK-1454 Pharmacodynamics ^b	X			X						X°	Cytokine and CRP samples should be obtained predose on C1D1, C2D1 and C5D1, either both in the morning (8 AM to 12 PM) or both in the afternoon (1 PM to 5 PM). Postdose serum samples for cytokine panels and CRP will be collected on C1D1, C2D1, and C5D1, and if applicable, on Day 1 of the first cycle that the subject has undergone intrasubject dose escalation of MK-1454. Postdose samples will be collected at 4 h (\pm 15 min) and 6 h (\pm 15 min) after MK-1454 administration. On C1D1, an additional serum sample will be collected at 12 h (\pm 2 h) and 24 h (\pm 4 h) following MK-1454 administration. Collect samples at the same time as for MK-1454 PK when feasible.

Protocol/Amendment No.: 001-08

Trial Period	MK	-1454 a		K-1454 nbroliz	Monotl						
Cycle		Cvcle 1			Cycle 2			Cycle 3			Notes
Scheduling Day	1	8	15	1	8	15	1	8	15	Beyond 1	11000
Scheduled Window	±3	±3	±3	±3	±3	±3	±3	±3	±3	±3	

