Plasma MK-1454 PK b,c	X			X						X°	Collect predose samples 1-8 h before MK-1454 administration on C1D1 and C2D1. Collect postdose samples on C1D1 and C2D1 at the following time points: end of IT injection (up to +15 min), 0.5 h (±15 min), 1 h (±15 min), 1.5 h (±15 min), 4 h (±15 min), and 6 h (±15 min). Additional postdose samples will be collected at 12 h (±2 h) and 24 h (±4 h) following MK-1454 IT administration on C1D1 only. If applicable, collect on Day 1 of the first cycle that the subject has undergone intrasubject dose escalation of MK-1454. Collect samples at the same time as for cytokines and CRP, and for pembrolizumab PK, when feasible.
Serum for Pembrolizumab PK	X			X						X	Pembrolizumab PK and ADA are for pembrolizumab-
Serum for ADA	X			X						X	treated subjects only. Collect samples predose 0 to 4 h before pembrolizumab IV infusion on C1D1, C2D1, C4D1, and on Day 1 of every 4 cycles thereafter (ie, C8, C12, etc.). Collect pembrolizumab and MK-1454 PK samples together, when feasible.
Blood for Plasma Biomarker Analysis				X						X	Collect prior to MK-1454 administration (Arm 1) and prior to pembrolizumab administration (Arm 2) on C2D1 and
Blood for Serum Biomarker Analysis				X						X	C5D1.
Blood for RNA Analysis	X									с	Collect predose 0-4 h before MK-1454 administration on C1D1. Collect postdose 6 h (±15 min) after MK-1454 administration on C1D1.
Blood for Genetic Analysis d	X										Collect prior to treatment.

Protocol/Amendment No.: 001-08

					Monot		Cycle =				
Trial Period	MK	-1454 a	ınd Per	nbroliz 	umab (Combin	ation Th	ierapy	Cycle =	Cycle 4	
Cycle		Cycle 1	ycle 1 Cycle 2		(Cycle 3			Notes		
Scheduling Day	1	8	15	1	8	15	1	8	15	1	
Scheduled Window	±3	±3	±3	±3	±3	±3	±3	±3	±3	±3	
Tumor Tissue Biopsy ^e									Х	X	For the tumor lesion that is treated with IT administration of MK-1454, collect postdose tumor biopsy on the same day as treatment, 5 h (\pm 2 h) following IT administration of MK-1454 on C3D15, and optionally on C6D1 at 5 h (\pm 2 h) following IT administration of MK-1454. Biopsy of a distant, discrete, noninjected site is preferred on the same day as the IT administration of MK-1454, but may be performed up to 3 days after treatment of the injected lesion. The C6D1 biopsy time point is encouraged, but optional.

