ADA = antidrug antibodies; AE = adverse event; aPTT = activated partial thromboplastin time; CBC = complete blood count; CRP = C-reactive protein; CT = computed tomography: CTCL = cutaneous T-cell lymphoma: ECG = electrocardiogram: ECOG = Eastern Cooperative Oncology Group: FBR = future biomedical research: GGT = gamma glutamyl transferase; hCG = human chorionic gonadotropin; HIV = human immunodeficiency virus; HNSCC = Head and Neck Squamous Cell Carcinoma; HPV = human papillomavirus; IEC = Institutional Ethics Committee; INR = international normalized ratio; IRB= Institutional Review Board; ISCL = International Society for Cutaneous Lymphomas; IT = intratumoral; LDH = lactate dehydrogenase; MRI = magnetic resonance imaging; PET = positron emission tomography; PT = prothrombin time: PTT = partial thromboplastin time: RNA = ribonucleic acid: RECIST v1.1 = Response Evaluation Criteria In Solid Tumors, version 1.1: irRECIST = immune-related RECIST; (F)T3 = (free) triiodothyronine; (F)T4 = (free) thyroxine; TSH = thyroid-stimulating hormone; WOCBP = women of childbearing potential.

- The inpatient observation period may be extended up to 48 hours at the discretion of the investigator, per local IRB/IEC, and/or Health Authority mandate.
- Up to 2 additional serum samples may be collected if deemed medically necessary (eg, in the setting of an AE).
- In the event a subject has undergone intrasubject dose escalation of MK-1454, these samples for biomarker analysis will be collected on Day 1 of the first cycle of the escalated new dose.
- This sample will be drawn for genetic variations in absorption, distribution, metabolism, and excretion (ADME) and planned analysis of the association between genetic variants in DNA and drug response. If the IRB/IEC does not approve of the planned analysis of the association between DNA variation and drug response, or if there is a local law or regulation prohibiting the same, then data analysis will be limited to investigate ADME genetic variations. If the sample is collected, leftover extracted DNA will be stored for FBR if the participant (or their legally acceptable representative) provides documented informed consent for FBR. If the planned genetic analysis is not approved, but FBR is approved and consent is given, then this sample will be collected for the purpose of FBR.

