CBC with Differential	X	X	X	X	X	X	X	X	
PT/INR and PTT or aPTT	X			X			X	X	D ' 1 '4' 701 (CIDI D 4 14 1 4 1'C
Chemistry Panel	X	X	X	X	X	X	X	X	Required within 72 h of C1D1. Does not need to be repeated if screening labs were done within 72 hours of C1D1. May be performed
LDH, GGT	X			X			X	X	up to 72 h prior to dosing for subsequent cycles when scheduled.
Urinalysis	X			X			X	X	up to 72 ii prior to dosnig for subsequent cycles when scheduled.
Lipase and Amylase	X			X			X	X	
Pregnancy Test for WOCBP – Urine or Serum hCG	X								Required within 24 h prior to first dose of study medication. Does not need to be repeated if screening test was done within 24 hours of C1D1. If a urine pregnancy test cannot be confirmed as negative, a serum pregnancy test is required. Pregnancy testing must be done as required by local regulation. Where local regulations require monthly pregnancy testing per CTFG guidelines, see Appendix 12.5.

Protocol/Amendment No.: 001-08

Trial Period				nothera	ру Сус			Q3W py Cycle =	
								Cycle 4 and	
Cycle	Cycle 1			Cycle 2			Cycle 3	Beyond	Notes
Scheduling Day	1	8	15	1	8	15	1	1	
Scheduled Window	±3	±3	±3	±3	±3	±3	±3	±3	
Thyroid Function (T4, FT4, T3, FT3, TSH)	X						X	X	To be performed within 72 hours prior to Day 1 of C1, C3, C5, C7, C9, C11, and at every other subsequent treatment cycle. Does not need to be repeated if screening labs were done within 72 hours of C1D1.
Pharmacokinetics (PK)/ Pharmacodynamics/ Future Biomedical Research/Biomarkers									See Procedures Manual for Collection and Management of Samples.
Serum for Cytokine Panel and CRP for MK-1454 Pharmacodynamics ^b	X			X				Xp	Cytokine and CRP samples should be obtained predose on C1D1 and C2D1 either both in the morning (8 AM to 12 PM) or both in the afternoon (1 PM to 5 PM). Postdose serum samples for cytokine panels and CRP will be collected on C1D1, C2D1, and C5D1. Postdose samples will be collected at 4 h (±15 min) and 6 h (±15 min) after MK-1454 administration. On C1D1, an additional serum sample will be collected at 12 h (± 2 h) and 24 h (± 4 h) following MK-1454 administration. Collect samples at the same time as for MK-1454 PK when feasible.

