Urinalysis	X	X			X			X			X	testing must be performed within 72 h prior to dosing when scheduled. Does not need to be repeated on C1D1 if
Lipase and Amylase	X	X			X			X			X	screening labs were done within 72 hours of C1D1.
Pregnancy Test for WOCBP – Urine or Serum hCG	X	X										Required within 24 h prior to first dose of study medication. Does not need to be repeated if screening test was done within 24 hours of C1D1. If a urine pregnancy test cannot be confirmed as negative, a serum pregnancy test is required. Pregnancy testing must be done as required by local regulation. Where local regulations require monthly pregnancy testing per CTFG guidelines, see Appendix 12.5.
Thyroid Function (TSH, T3, FT3, T4, FT4)	X	X						X			X	Required within 72 hours prior to Day 1 of C1, C3, C5, C7, C9, C11, and at every other subsequent treatment cycle. Does not need to be repeated on C1D1 if screening labs were done within 72 hours of C1D1.
HIV, Hepatitis B and C screen (per site SOP)	X											Include HCV antibody or HCV RNA (qualitative) and HBsAg.

MK-1454-001-08 Final Protocol 27-Jul-2021 Confidential

Protocol/Amendment No.: 001-08

Trial Period	Screening		Treatment Phase MK-1454 Cycle = COI then Q3W; or Q3W Pembrolizumab Cycle = 21 Days Cycle 4									
			~ .		_				~		and	
Cycle	20.4 4		Cycle		1	Cycle 2		_	Cyc		Beyond	Notes
Scheduling Day Scheduled Window	-28 to -1	1	8	15	1	8	15	1	8	15	1	
Scheduled Window	Lab	_	±3 ±3 ±3 ±3 ±3 ±3 ±3 ±3								See Procedures Manual for Collection and Management of Samples.	
Serum for Cytokine Panel and CRP for MK-1454 Pharmacodynamics ^b	X	X			X						X·	Cytokine and CRP samples should be obtained at Screening, and predose on C1D1, C2D1 and C5D1, either both in the morning (8 AM to 12 PM) or both in the afternoon (1 PM to 5 PM). Postdose serum samples for cytokine panels and CRP will be collected on C1D1, C2D1, and C5D1. Postdose samples will be collected at 4 h (±15 min) and 6 h (±15 min) after MK-1454 administration. Collect samples at the same time as for MK-1454 PK when feasible.
Plasma MK-1454 PK ^b		X			X						X	Collect predose samples 1-8 h before MK-1454 administration on C1D1 and C2D1. Collect postdose samples on C1D1 and C2D1 at the following time points: end of IT injection (up to +15 min), 0.5 h (±15 min), 1 h (±15 min), 1.5 h (±15 min), 4 h (±15 min), and 6 h (±15 min). Collect samples at the same time as for cytokines and CRP, and for pembrolizumab PK, when feasible.

Protocol/Amendment No.: 001-08

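### Arm 3 takes cytokine and CRP samples after the C5D1 dose but schedules no C5D1 predose sample, so the same-day change at that visit cannot be computed

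*Combined protocol and SAP*

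**What the plan says.** Section 4.2.3.4 describes the target-engagement measure as a "systemic cytokine/chemokine activation assay that compares a panel of cytokine/chemokine activation pre- and post-administration" of study drug. Section 7.1.3.2.3 leaves the sampling times to the Schedule of Activities, so the schedule notes are the only place in the protocol where they are set.

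For Arm 3, Section 6.1.3 names C1D1 and C2D1 as the predose visits: "Cytokine and CRP samples should be obtained predose on C1D1 and C2D1 either both in the morning". The next sentence reads: "Postdose serum samples for cytokine panels and CRP will be collected on C1D1, C2D1, and C5D1". The C5D1 postdose samples fall at 4 h and 6 h. For Arms 1 and 2, Section 6.1.2 says "Cytokine and CRP samples should be obtained predose on C1D1, C2D1 and C5D1, either both in the morning". For Part II, Section 6.2.1 says "Cytokine and CRP samples should be obtained at Screening, and predose on C1D1, C2D1 and C5D1".

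Section 6.1.2 also ties sampling to intrasubject dose escalation. Its cytokine note adds a draw "on Day 1 of the first cycle that the subject has undergone intrasubject dose escalation of MK-1454", its PK note says "If applicable, collect on Day 1 of the first cycle that the subject has undergone intrasubject dose escalation of MK-1454", and a footnote repeats the rule: "In the event a subject has undergone intrasubject dose escalation of MK-1454, these samples for biomarker analysis will be collected on Day 1". Section 6.1.3 has no such rule. Its grid marks plasma MK-1454 PK under Cycle 4 and beyond, but the note gives times for C1D1 and C2D1 only. The footnote on that cell covers up to two extra serum samples if medically needed.

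On whether an Arm 3 subject may escalate at all, the protocol disagrees with itself. Sections 1.0, 2.1.1 and 5.2.4 allow it for subjects in the accelerated titration (ATD) phase after three cycles, and Sections 1.0 and 5.2.4 limit it to once. Section 4.2.2.3 rules it out for Parts E and F.

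**The concern.** A postdose cytokine value is most informative as a change from a value taken just before the same dose. At C5D1 in Arm 3 that value is not scheduled, although the two sister schedules have it and the protocol gives no reason for the difference. C5D1 is the only cytokine visit named after Cycle 2, so it is the only planned look at whether the acute response to a dose persists. Without a same-day baseline, the effect of the C5D1 dose is mixed with whatever shifted over the preceding weeks of MK-1454, pembrolizumab and disease.

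The data have some use. Section 2.1.1 lets exposure and pharmacodynamic data modify the recommended dose. Section 4.2.2.5 shows that IP-10, one of the analytes listed in Section 4.2.3.4, was considered when the Cohort A and B dose was chosen. Arm 3 supplies the dose and frequency for Cohort C.

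The untimed PK entry is a practical problem: a site cannot tell from Section 6.1.3 when, or whether, to draw that sample. MK-1454 PK is a secondary objective (Section 3.2).

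**Working it through.** No sample size, power or error rate depends on this point, so the check is a comparison of the three schedules plus calendar arithmetic.

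**Cytokine and CRP sampling by schedule**

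| Schedule | Predose visits in Cycles 1 to 5 | Postdose visits | Same-day pairs |
|---|---|---|---|
| Arms 1 and 2 (6.1.2) | C1D1, C2D1, C5D1 | C1D1, C2D1, C5D1 | 3 |
| Arm 3 (6.1.3) | C1D1, C2D1 | C1D1, C2D1, C5D1 | 2, plus an unpaired C5D1 set |
| Part II (6.2.1) | C1D1, C2D1, C5D1 | C1D1, C2D1, C5D1 | 3 |

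A screening sample is also taken in all of these groups (Sections 6.1.1 and 6.2.1).

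**Age of the possible substitute baselines at C5D1 (21-day cycles)**

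- C5D1 is day 4 × 21 + 1 = 85, and C2D1 is day 21 + 1 = 22.
- From C2D1: 85 − 22 = 63 days, or 9 weeks. With the ±3-day window at each visit, the range is 63 − 6 = 57 to 63 + 6 = 69 days.
- From C1D1: 85 − 1 = 84 days, or 12 weeks.
- From screening (1 to 28 days before C1D1): 84 + 1 = 85 to 84 + 28 = 112 days, or just over 12 to 16 weeks.

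So the most recent substitute is nominally 9 weeks old. It follows one cycle of treatment, whereas the C5D1 dose follows four.

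**Draws tied to intrasubject escalation**

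- Section 6.1.2 has two kinds, cytokine and PK. Section 6.1.3 has none.
- Three cycles must be completed first, so the earliest escalated dose is C4D1, on day 3 × 21 + 1 = 64. A subject escalated at C4D1 or C5D1 still has C5D1 postdose cytokines at the new dose, without a same-day baseline. PK at that dose has no stated time.
- Subjects concerned: Section 8.9.1 assumes 2 possible ATD dose cohorts in Arm 3, each with 1 and at most 3 subjects. That gives 2 × 1 = 2 to 2 × 3 = 6, out of 34 in that scenario (about 35 planned).

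**The case against.** The strongest reply is that little is lost. Cytokines serve exploratory aims, and the TNF-α trigger for leaving the ATD phase applies only to Arms 1 and 2 (Section 5.2.1.2), so no Arm 3 rule turns on the missing tube. Screening, C1D1 and C2D1 baselines all exist. An escalating subject may move only to a level already cleared for DLT, and subjects allocated to that level have C1D1 and C2D1 cytokine and PK profiles. Section 4.2.2.3 may mean that there are no such subjects. All of this stands, and it keeps the point small. It does not explain why the C5D1 postdose samples are drawn in Arm 3 without the baseline that the other schedules provide.

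A reader might infer more than the documents support:

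- That late cytokine change in Arm 3 cannot be measured at all. Only the same-day change is lost; change from an older baseline remains available.
- That Arm 3 has no data at an escalated dose. The C5D1 postdose cytokines can fall at that dose, and the Cycle 4 and beyond PK entry is ambiguous rather than absent.
- That a comparison of visceral with superficial injection is spoiled. Section 3.0 sets no such objective, the arms are not randomized, and their dosing frequencies differ, so a paired C5D1 sample would not make that comparison clean.
- That the Cohort C dose choice is undermined. That choice draws on exposure, safety, pharmacodynamics and clinical benefit together.

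**Conclusion.** The point holds in a narrow form. Followed as written, Section 6.1.3 leaves every Arm 3 C5D1 postdose cytokine and CRP set without a same-day baseline. The number of subjects is the number reaching Cycle 5 out of about 35; the documents do not give that number. The nearest alternative baseline is nominally 9 weeks old. This is a schedule misalignment in exploratory data and does not threaten the primary or secondary conclusions.

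The untimed PK entry is a separate inconsistency between grid and note. The missing escalation draw is conditional: it matters only if Arm 3 escalation is permitted, and then for about 2 to 6 subjects on the Section 8.9.1 scenario.

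This reading assumes that the schedule notes govern sampling. The Procedures Manual and the supplemental SAP are not among the documents and might say more.

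**What to change.** 1. In Section 6.1.3, add C5D1 to the predose cytokine and CRP visits, to match Sections 6.1.2 and 6.2.1. Arm 3 already has plasma and serum biomarker blood drawn on C5D1 before pembrolizumab, so the cost is one extra tube at that draw, subject to the existing morning-or-afternoon rule.
2. Give the Cycle 4 and beyond entry for plasma MK-1454 PK in Section 6.1.3 a defined visit and times, or remove it. Removing it costs only the edit.
3. Reconcile Section 4.2.2.3 with Sections 1.0, 2.1.1 and 5.2.4 on intrasubject escalation in Arm 3. Only if escalation is permitted, carry over the Section 6.1.2 rule for PK and cytokine sampling on Day 1 of the first cycle at the escalated dose. If the C2D1 PK series is used, that is seven samples per subject (predose, end of injection, and 0.5, 1, 1.5, 4 and 6 h) plus the cytokine tubes, in about 2 to 6 subjects.
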